## 4 STUDY EVALUATIONS AND MEASUREMENTS

### 4.1 Efficacy Evaluation

#### 4.1.1 Primary Outcome

**Opioid dose**, as measured by prescribed milligrams of daily MED, is the primary study outcome. The primary outcome will be examined at baseline and months 6, 12, and 18 using opioid prescription data (**Table 3**). Prescribing data (including drug name, start and stop dates, dose, and frequency) will be derived from the EHR and provided by the PCORnet STAR CRN warehouse common data model (CDM). The field generally accepts prescribing data as documenting ingestion; other current and previously published studies also use prescribed dose as the primary endpoint. However, we recognize that ingestion may not be the same as the prescribed regimen. We will analyze the absolute (primary) decrease (or increase) in opioid MED from the baseline period (average of 90 days prior to randomization) until 18 months after randomization. We also will examine percentage decrease. Total morphine equivalents for each prescription will be calculated by multiplying the quantity of each prescription by the strength of the prescription (milligrams of opioid per unit dispensed). The quantity-strength product is then multiplied by conversion factors derived from published sources to estimate the milligrams of morphine equivalent to the opioids dispensed in the prescription. The total average dose in morphine equivalents per day supplied is calculated by summing the morphine equivalents for each prescription filled during a given period and dividing by the number of days supplied.

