#### 4.1.4 Other EHR-Derived Outcomes

*Cross-reference: UNC IRBIS Application section A.9.1 (identifiers).*

Other measures collected through the PCORnet CDM include:

- Demographic information (birth date, sex, race, and ethnicity)
- Patient height and weight
- Health care provider information
- Death information (death date and source)
- Health care visit information (visit dates, primary payer, facility type, and provider ID)
- Diagnosis and condition information (condition data and type, diagnosis dates, and associated ICD/CPT codes) for:
  - Mental health disorders, defined by ICD-10 codes (e.g., depression, anxiety, schizophrenia, bipolar disorder, suicide attempt/intent)

- Number and type of CNCP conditions per ICD-10 codes (e.g., back pain, neck pain, headache, arthritis, HIV)
- Alcohol/substance misuse or abuse as measured by ICD-10 codes.
- Overall comorbidity using the Charlson Comorbidity Index per ICD-10 codes
- Opioid prescription information including RxNorm CUI (drug prescribed), prescription dates, dose, units, frequency, route, quantity, refills, and supply days.

We will calculate time to discontinuation of opioids, where discontinuation will be measured based on our previous work, except that the discontinuation will be defined as the first day of a minimum 90-day period with no opioid prescriptions (see Section 5.2 for additional information about the definitions and analyses).

A Schedule of Assessments indicating the timing and source of efficacy, safety, and fidelity measures is presented in **Table 6**.

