3.2 Outcomes

3.2.1 Primary Outcome

The primary outcome is **change from baseline in average daily opioid dose in MED**. The daily MED for each prescription will be calculated by multiplying the quantity of each prescription by the strength of the prescription by the MED conversion factor and dividing it by the total days supply. The primary outcome will be examined at baseline and months **3, 6, 9, 12, 15 and 18** using opioid prescription information recorded in the EHR from 90 days prior to randomization until 18 months after randomization, as provided by the PCORnet common data model (CDM) data warehouse at each site. For each timepoint, the primary outcome will be derived including all opioid medications prescribed 90-days prior to the desired timepoint. The primary timepoint is 12 months; key secondary timepoints at 6 and 18 months.

Derivation of this outcome is provided in section 9.2.

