5.2 Per-Protocol Population

As in most pragmatic clinical trials, some participants may not adhere to the intervention they were randomized to receive, reducing fidelity to the intervention as designed and potentially changing the effectiveness of the intervention. The most likely form of nonadherence will be absence from group therapy sessions in the MI+CBT-CP arm or with patients in the SDM arm ceasing interaction with the assigned provider. The potential impact of this nonadherence is underestimating the magnitude of the true treatment effect. To assess this, in addition to the ITT analyses, we will also conduct secondary analyses using a per protocol population consisting of participants that met all inclusion/exclusion criteria, and received a substantial portion of the randomized intervention, defined as at least 4 completed SDM visits and at least 4 completed MI or CBT sessions (out of a total of 1 MI and 8 CBT). Note that the inclusion criterion for baseline MED is based on the most recent prescription, while the baseline value for MED in the analysis is the average MED for the past 90 days. Having a baseline value < 20 is not a protocol violation when the sites indicated that inclusion criterion was met based on the most recent prescription when the patient was assessed. A sensitivity analysis on the per-protocol population will also be conducted by defining this population as those who met all inclusion/exclusion criteria and completed at least 3 SDM visits and at least 3 MI or CBT sessions. This sensitivity analyses are included as many SDM participants may only complete 3 visits with their provider throughout the 12-month intervention phase in the event their opioid prescriptions can be renewed over a 3-month period without an actual clinic visit.

The per-protocol analysis provides a better estimate of the true efficacy of an intervention (i.e., among those who completed the treatment as planned) (Ranganathan, Pramesh, & Aggarwal, 2016). No other analysis populations are defined for this protocol.

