9.2 Variable Definitions

The table below provides a description of the study endpoints and subgroup categories, including data type and derivation. More information regarding these variables is provided in the analysis dataset specification file.

Variable	Type	Definition
Primary Outcome		
Change in opioid dose (based on average daily MED) from baseline to 12 months post-randomization	Continuous	
The primary outcome will be derived from EHR data from the Mid-South CDRN data warehouse. Total morphine equivalents for each prescription will be calculated by multiplying the quantity of each prescription by the strength of the prescription (milligrams of opioid per unit dispensed). The quantity-strength product is then multiplied by conversion factors to estimate the milligrams of morphine equivalent to the opioids dispensed in the prescription. The total average dose in morphine equivalents per day supplied is calculated by summing the morphine equivalents for each prescription filled during a given period and dividing by the number of days supplied. The below algorithms further describe derivation of the primary outcome measure:
 $\text{One Prescription's MED Daily (MEDD)} = \frac{(\text{Strength per unit}) \times (\text{Quantity dispensed}) \times (\text{MME Conversion factor})}{(\text{Days Supply})}$ $\text{Avg. MEDD per Timeframe} = \frac{(\text{Multiply each RX's MEDD by Days Supply}) \text{ then } (\text{Sum all RX's Total MEDD for those prescriptions within timeframe})}{\text{Total number of days in timeframe}}$ 
Opioid dose will be calculated as the prescribed milligrams of daily MED averaged over the 90 days prior to randomization and averaged over 90-days for the time periods of 3, 6-, 9-, 12-, 15- and 18-months post randomization.
 
We expect no missing prescriptions, yet some participants might not have complete data because (a) they discontinued and removed consent to use data after that date, (b) they were lost to follow-up and may have moved out of the clinic's care, (c) the last CDM transfer did not contain their data up to 18 months past baseline or (d) they discontinued taking opioids. Cases of (d) will be identified by the response to the T2 and T3 survey item G20 "Are you currently taking an opioid medicine now?". If the response indicates "no" and opioid prescriptions last dose date ends before month 18, then an MED of zero will be assumed for all days after the last dose date to Month 18 (or date participant removed informed consent, if applicable). Otherwise, if there is not a "no" response

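### The displayed primary-outcome formula in SAP 9.2 has no refill term, so if quantity is per fill an order with refills is under-counted, and the prose gives a conflicting denominator

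*SAP*

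**What the plan says.** - **Per-order total.** SAP 9.2: "Total morphine equivalents for each prescription will be calculated by multiplying the quantity of each prescription by the strength of the prescription", times a conversion factor. SAP 3.2.1 describes the daily dose of one prescription as "multiplying the quantity of each prescription by the strength of the prescription by the MED conversion factor and dividing it by the total days supply". Neither has a refill term, and nor does Protocol 4.1.1.
- **Period average.** The displayed formula in SAP 9.2 re-multiplies each prescription's daily dose by its days supply, sums over the window and divides by "Total number of days in timeframe". The prose just above it ends by "dividing by the number of days supplied", as does Protocol 4.1.1.
- **Source.** Protocol 4.1.1: "Prescribing data (including drug name, start and stop dates, dose, and frequency) will be derived from the EHR". SAP 3.2.1 selects the opioids for each timepoint by when they were prescribed, over the preceding 90 days. Yet the displayed formula labels its quantity term "Quantity dispensed".
- **Available fields.** Protocol 4.1.4 lists "Opioid prescription information including RxNorm CUI (drug prescribed), prescription dates, dose, units, frequency, route, quantity, refills, and supply days", so quantity, refills and supply days are three separate items.
- **Inputs allowed.** Protocol 5.3.3 (Missing Data) restricts the derivation to the drug, its strength and the pill count.
- **Where the rules should be.** SAP 7.3 says that the assumptions behind daily MED and days supply are all in Section 9.2. That section gives no refill rule.

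**The concern.** The displayed formula spreads the drug in an order over every day of the window. If one order covers three months through refills but its quantity describes one month, the other two months count as zero dose. A later window supplied only by refills of an earlier order contains no order and receives nothing. SAP 9.2's rule for missing or zero days acts only after the last dose date, so it does not repair gaps between orders.

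This enters the sole primary endpoint. The SAP expects some renewal without visits: SAP 5.2 allows for few SDM visits "in the event their opioid prescriptions can be renewed over a 3-month period without an actual clinic visit". Ordering habits could also differ by arm. Under Protocol 6.2.1 an Arm 1 participant may move to an SDM-trained prescriber, and visits may become more frequent when the dose changes. Under Protocol 6.3.1 an Arm 2 participant keeps the same prescriber. If the shift in ordering pattern differed between arms, it would read as a difference in dose reduction.

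**Working it through.** **The plan's own figure.** SAP 6 and 7.6 give a difference of 10 MED, SD 40, two-sided 0.05 and 80% power. The normal approximation gives 252 per arm. The t-based solution is 252.1, which rounds up to 253 per arm (506 in total), as stated. Power at 253 per arm is 80.3%. The documents give no figure for the effect of refills.

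**Inputs for the example.** Dose of 55 MED/day (planning mean, Protocol 5.4); 30 days per order (the usual run-out in Protocol 5.2.3); 90-day window (SAP 9.2). Two refills per order is an assumption, as is quantity per fill.

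**Formula.** In the displayed algorithm days supply cancels:

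average = sum of (strength × quantity × factor) / 90 = sum of (daily dose × days in one fill) / 90

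**One stable participant at 55 MED/day:**

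| Orders in the window | Displayed formula | Result |
|---|---|---|
| Three 30-day orders | 55 × 90 / 90 | 55.0 |
| One 30-day order, 2 refills | 55 × 30 / 90 | 18.3 |
| Same order, refills counted | 55 × 30 × (1 + 2) / 90 | 55.0 |
| No order, supplied by earlier refills | 0 / 90 | 0 |

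The one-third ratio does not depend on dose: 20 becomes 6.7 and 90 becomes 30.

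**Effect on change from baseline.**

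- Monthly orders at baseline, refilled order at follow-up: 18.3 − 55.0 = −36.7 MED, a false fall.
- Refilled at baseline, monthly at follow-up: +36.7 MED, a false rise.
- Same pattern at both: change 0, with both levels understated by two thirds.

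**Prose denominator.** Dividing by days supplied, the refilled order gives 55 × 30 / 30 = 55 MED, with no loss. A window containing no order would then have zero over zero.

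**Arm contrast.** If the share of participants who switch from monthly to refilled orders differs between arms by g, the bias is g × 36.7:

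- 5 points: 1.8 MED
- 10 points: 3.7 MED
- 20 points: 7.3 MED
- For a false 10 MED: 10 / 36.7 = 27 points

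**Equal switching in both arms.** There is no bias, but variance is added: SD = √(40² + p(1 − p) × 36.7²). For p = 5%, 10% and 20% the SD is 40.8, 41.5 and 42.6. Power at 253 per arm falls from 80.3% to 78.7%, 77.4% and 75.2%.

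**The case against.** Several stronger readings are tempting, and the documents do not support them.

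- A reader might infer that every statement of the formula loses two thirds of a refilled dose. Only the displayed period average does. The prose in SAP 9.2 and Protocol 4.1.1 divides by days supplied, and SAP 3.2.1 divides each prescription by its own days supply. If quantity and days supply both describe one fill, refills cancel there. The displayed formula probably governs, because SAP 9.2 presents it as the fuller description and says doses are averaged over 90 days. But the conflict is real, and the size of the problem depends on how it is resolved.
- A reader might infer that refilled orders are common. Protocol 5.2.3 points the other way: it treats a prescription within 120 days as equivalent to run-out within 90, which implies that an order lasts about 30 days. The renewals in SAP 5.2 may be new orders, which the formula counts correctly. Extracting a refill field does not show that it is populated.
- A reader might infer that the last dose date falls 60 days early (2 × 30). SAP 9.2 does not define that date, and stop dates are among the fields named in Protocol 4.1.1, so it may not be computed from quantity at all.
- A reader might infer that the program ignores refills. SAP 9.2 refers to a dataset specification file that is not among the documents and might handle them.

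There is also a partial safeguard. SAP 4.4.3 checks for average baseline MED below 20, so a 55 MED participant scored at 18.3 would be reviewed. No such check is stated for follow-up windows.

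These points limit the size and certainty of the problem. They do not supply the missing rule, which SAP 7.3 places in Section 9.2.

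**Conclusion.** The point holds conditionally and should be fixed before the final analysis. Followed as printed, the displayed formula gives a 30-day order with 2 refills one third of its dose, provided the recorded quantity is per fill and refills are not expanded elsewhere. A false change then requires a different ordering pattern at baseline and follow-up, and a biased arm contrast requires that shift to differ by arm.

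The size in this trial is unknown. The range of 1.8 to 7.3 MED rests on assumed imbalances of 5 to 20 points at 55 MED/day, and a false effect as large as the planned 10 MED needs about 27 points. The documents therefore do not show that the primary comparison is biased. They show that a step in the sole primary endpoint is undefined for orders with refills, and that SAP 9.2 states two denominators giving different answers for the same order (18.3 and 55 MED in the example).

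**What to change.** In SAP 3.2.1 and 9.2:

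1. Reconcile the two denominators and state which one governs.
2. Check at each site whether quantity and supply days in the common data model already include refills, and record the answer. If they do not, use quantity × (1 + refills) and days supply × (1 + refills). Lay the supply forward from the start date, split it across windows, and end it at the recorded stop date or at the order that replaces it. If they already include refills, apply no multiplier, since that would over-count.
3. Define the last dose date from the same supply.
4. Tabulate refill frequency by arm and window, and report the primary result with and without refills as a sensitivity analysis.

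Protocol 5.3.3 limits the inputs to three fields, so the SAP should note the departure if refills are added. The cost is SAP wording, a query to the sites and a few lines of derivation code, since the fields are already extracted. The drawback is that some authorised refills may never have been filled; comparing results with and without refills shows how much that matters.

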4.6 Database Lock

As noted above, 3 different study databases will provide data. The last participant is expected to be enrolled in March 2022 and the last intervention visit may go until March 2023. The last T2 (6-month) survey is expected in September 2022 and the last T3 (12-month survey) is expected in March 2023. The T2 and T3 survey database will be locked approximately one month after the last completion of the T3 survey. The REDCap database lock will occur after the last participant's final intervention status CRF has been completed (i.e., completed the 12-month intervention phase) and all data queries have been resolved by the study sites. As mentioned above in section 4.4.3, the EHR data extraction takes places 3 times across the study. *Although the final EHR data extraction is planned to take place in July or August 2023, or 18-months after the last participant was enrolled into the study, it will likely not contain 18-months of EHR data for the last participant since there is up to a 3-month lag between clinic visit and data inclusion in the CDM. However, all participants should contain 12-months of EHR data in the final extraction (the study's primary timepoint).* The final EHR data extraction will be considered final and locked after the sites have addressed any potential RTI queries and transferred a clean dataset (expected to occur ~2-months after the initial data transfer). The locked datasets from each of the 3 databases will be used to derive the final analysis dataset which will be used to perform the analyses described within this SAP. Analysis data specifications are further described in section 9.2.

The study is designed as intention-to-treat (ITT). If a participant discontinues further intervention or participation in the study, every attempt will be made to continue to perform the required study-related follow-up surveys and EHR data extraction. However, surveys and EHR data will not continue to be collected from those who are determined ineligible, withdrew from all study activities, investigator withdrew and other (depending on the reason).

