6. SAMPLE SIZE DETERMINATION

Sample size estimates were generated to provide robust power to detect minimal clinically important differences (MCID) in reduction of opioid use between the 2 study arms.

A total sample size of 506 participants (253 per study arm) will provide 80% power to detect an effect size of a difference of 10 MED between the SDM and MI+CBT intervention arm using an analysis of covariance model with $\alpha=0.05$ and assuming a baseline model-adjusted standard deviation for change from baseline of 40 MED. The sample size was inflated by 20% (608 total participants; 304 per study arm) to account for potential variance inflation associated with CBT group delivery (based on a group

size of 8 and an interclass correlation coefficient of 0.01) and a potential loss of follow-up opioid prescription data on as many as 12% of participants.

For the PROMIS secondary outcome measures, the minimally important difference (MID) for the physical function scale is 2 units, whereas the MID for the pain interference scale is 3.5 units. For both instruments, we assume the standard deviation for change from baseline is 10 (see section 9.2 for a more thorough description of these secondary measures). With the planned total of 608 randomized participants and assuming 20% of those have missing PROMIS scale responses, the power for the PROMIS Pain Interference score is 96%, while the power for the PROMIS Physical Functioning scale is 57% (Table 6.1).

Note that the enrollment was slower than planned, and due to timeline constraints was stopped prior to reaching 608 randomized participants. Final study enrollment was 526 randomized participants. As of June 2023 (DSMB report), study discontinuation was at 20%;, but survey completion rate was tracking around 60% (40% missing, higher than the planned levels). Approximate post-hoc power based on the final sample size is provided in Table 6.1.

Table 6.1. Power for Primary and Key Secondary Outcomes

Total sample size	Primary aim: Power for opioid MED ¹	Secondary aim: power for PROMIS Pain Interference ²	Secondary aim: Power for PROMIS Physical Functioning ²
Planned 608	80%	96%	57%
Approximate post hoc power based on randomized (n=526)	75% based on protocol- assumed level of missing opioid prescription data	85% Based on number of completed surveys	40% Based on number of completed surveys

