
Variable	Type	Definition
		
to this item at the applicable T2 or T3 survey, or the survey was not completed, then the data after the last dose date ends will be considered missing in the calculation of the average MED across the 3-month time intervals.
 
NOTE: Section 5.3.1 in the protocol states the time periods of 4-, 6-, 8-, 10-, 12-, 14-, 16-, and 18- would be used; however, that was an inadvertent typo and it is correctly stated in protocol section 5.2.1.
 
For each of the post-randomization periods, change in daily opioid dose will be computed as the difference between the dose calculated during that period and the dose from the baseline period.
 
Further documentation regarding the medications included in the derivation of average daily opioid dose (MED) can be found in the supplemental file titled “INSPIRE_SAP_Suppl_Opioid_Meds”

Average percentage change in MED (based on average daily MED) from baseline period	Continuous	Percent change is calculated as the change from baseline divided by the baseline value. For example, if average baseline is 30 and average post baseline is 20, percent change is $(20-30)/30 =$ decrease of 33%. Alternatively, if average baseline is 30 and average post baseline is 40, average percent change is $(40-30)/30 =$ increase of 33%.
Average relative amount of MED from baseline (based on average daily MED)	Continuous	
If warranted based on evaluation of the data prior to database lock, we may evaluate average relative change rather than actual change – defined as the value in the post baseline timepoint divided by the baseline value.
 
For example, if average baseline is 30 and average post baseline is 20, average relative change is $20/30 = 2/3$rds of the average baseline MED.
 
If determined not warranted, this variable will not be calculated.

Indicator for change from BL of at least 10 MED	dichotomous	Calculated at 3, 6, 9, 12, 15, 18
Secondary Outcomes		

Variable	Type	Definition

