9.3 Analysis of the Primary Outcome

The intervention effect on opioid use over time will be assessed using a linear mixed model for repeated measures (MMRM) using categorical time effects (ref: S Davis). The model will be used to generate point and interval estimates and to test differences in mean changes in opioid dose between the 2 intervention groups at 12 months (primary timepoint) and 6 and 18 months (secondary timepoints). While the primary and secondary time assessments are at 6, 12 and 18 months, all available opioid prescription data from baseline (3-month average before randomization) through 18 months will be included in the model. The model will include fixed effects for the intervention group, time interval (as a categorical variable for **3, 6, 9, 12, 15 and 18**), intervention-by-time interaction, baseline opioid dose, and the stratification effect of institution (see model statement below). For each of the post-baseline timepoints, the daily MED is the average of the time from the end of the prior interval (i.e., 12 months is the 3-month average between 9 and 12 months). (Note: an inconsistency in the protocol inaccurately lists these intervals in protocol section 5.3.1, but they are accurately listed in Protocol Section 5.2.1).

This approach will provide consistent estimates and valid inferences under missing at random (MAR) data assumptions while accounting for correlation among multiple measures on the same participant. This mixed model will improve the power of the study and the precision of all estimates by allowing all available measures for an individual to be incorporated in the analysis, even if other timepoints are missing. An intervention-arm-specific Toeplitz correlation structure will be assumed for the within-participant measures, to reflect the changing correlation of these measures over time and permit the correlation structure to differ between study arms. Note: if this model does not converge, then a Toeplitz (not intervention-specific) structure will be fit. This model is further described below:

$$Y_{ij} = \alpha + \beta_1 Time_{ij} + \beta_2 Site_{ij} + \beta_3 Intervention_{ij} + \beta_4 BaselineOpioidDose_{ij} + \beta_5 (Intervention \times Time)_{ij} + \epsilon_{ij}$$

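### The primary opioid-dose definition gives two different divisors, and its printed formula keeps days declared missing in the denominator, scoring them as zero

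*SAP*

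**What the plan says.** SAP 9.2 describes the primary outcome first in prose: the period dose comes from "summing the morphine equivalents for each prescription filled during a given period and dividing by the number of days supplied". Protocol 4.1.1 has the same sentence. Two formulas follow in the SAP cell. The first gives one prescription's daily MED, dividing by its days supply. The second multiplies each daily MED back by its days supply, sums over the window and divides by "Total number of days in timeframe". The cell then says the dose is averaged over 90 days. Protocol 5.2.1 also uses a 90-day average, and SAP 9.3 explains that "12 months is the 3-month average between 9 and 12 months".

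For days after the last recorded dose, SAP 9.2 has two rules. If survey item G20 (currently taking an opioid) is answered no, those days are zero. Otherwise "the data after the last dose date ends will be considered missing in the calculation of the average MED" over the three-month intervals. Neither rule mentions the denominator, and no minimum number of usable days is set.

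Partly observed windows are foreseen. SAP 9.2 lists withdrawn consent, leaving the clinic's care and an incomplete last transfer. SAP 4.6 says of the final extraction that "it will likely not contain 18-months of EHR data for the last participant since there is up to a 3-month lag", although 12 months of data are expected for everyone. SAP 6 reports that "survey completion rate was tracking around 60% (40% missing, higher than the planned levels".

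SAP 9.2 also notes: "More information regarding these variables is provided in the analysis dataset specification file". That file was not available.

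**The concern.** This is the trial's only primary variable, and its text supports more than one value for the same patient.

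- **Days supplied against calendar days.** Dividing by days supplied measures dose while supplied, so gaps in supply do not lower it. Dividing by calendar days measures average exposure, so gaps do lower it. A patient who moves to intermittent prescriptions shows no change on one definition and a large fall on the other.
- **Missing days.** The formula's denominator is fixed at the window length. A day declared missing adds nothing to the numerator but still counts in the denominator, so it acts as a zero. In the window where the last prescription runs out, a patient who said they had stopped and a patient with no information then get the same value. Missing data become apparent dose reduction.

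A missing survey cannot supply a G20 no, so the missing rule, not the zero rule, applies to those patients.

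**Working it through.** **The plan's own figure.** Difference 10 MED, adjusted SD 40, two-sided 0.05, 80% power (SAP 6 and 7.6): n = 2 × (1.960 + 0.842)² × 40² / 10² = 251.2, so 252 per arm. The t-based value is 252.1, rounded up to the plan's 253. Power at 253 per arm by normal approximation is 80.3%. This figure is not in dispute. It sets the scale.

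**Inputs.** 55 MED/day is the planned mean dose (Protocol 5.4). Prescriptions are taken as 30 days (Protocol 5.2.3 says generally 30). The window is 90 days (SAP 9.2).

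**Sentence against formula.**
- Baseline, three prescriptions: 3 × 30 × 55 = 4,950. Divided by 90 days supplied: 55. Divided by 90 calendar days: 55.
- Month 12, one prescription: 30 × 55 = 1,650. Divided by 30 days supplied: 55. Divided by 90 calendar days: 18.3.
- Change: 0 by the sentence, -36.7 by the formula. This applies where the uncovered days are not missing (a later prescription exists, or G20 is no).

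**Missing days in the denominator.** Assume constant dose, continuous supply up to run-out day r, no G20 no, and r spread evenly over days 1 to 89. The denominator effect s is the value over the r non-missing days minus the value over 90 days, with the numerator unchanged. It depends on how supply is credited.

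- *Whole prescriptions credited to the window in which they are ordered.* This is what SAP 3.2.1 implies by "including all opioid medications prescribed 90-days prior to the desired timepoint". Let k be the number of prescriptions ordered in the window: 0 for r = 1-29, 1 for r = 30-59, 2 for r = 60-89. Then s = k × 1,650 × (1/r - 1/90). Example, r = 40: 1,650/90 = 18.3 against 1,650/40 = 41.25. The mean of s over r = 1-89 is 9.6 MED, or 14.2 if at least one prescription was ordered in the window.
- *Supply credited day by day.* s = 55 × (90 - r)/90. Mean 27.5 MED, minimum 0.6.

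**Effect on an arm.** For an assumed share f affected equally in both arms, the shift is f × mean(s), and the SD is √(40² + f × mean(s²) - (f × mean(s))²). Mean(s²) is 191.5 for whole prescriptions. For day-level supply it is (55/90)² × 2,685 = 1,002.7. Example, day-level, f = 10%: SD = √(1,600 + 100.3 - 7.6) = 41.1, power 78.0%.

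| Share affected | Overstated change, whole prescriptions | Power | Overstated change, day-level | Power |
|---|---|---|---|---|
| 2% | 0.2 MED | 80.2% | 0.6 MED | 79.8% |
| 5% | 0.5 MED | 80.1% | 1.4 MED | 79.1% |
| 10% | 1.0 MED | 79.8% | 2.8 MED | 78.0% |

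The contrast between arms moves only if the shares differ. A 5-point difference would move it by 0.05 × 9.6 = 0.5 MED or 0.05 × 27.5 = 1.4 MED.

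**The case against.** The best defence is that the intent is clear. The formula, the 90-day text, Protocol 5.2.1 and SAP 9.3 all point to a calendar-day average, so the days-supplied sentence is a leftover. An average in which some data are called missing is ordinarily taken over the rest, and the SAP takes care to separate zero from missing. The specification file may say so outright. The primary timepoint is also fairly safe from late extraction, because SAP 4.6 expects 12 months of EHR data for all. The survey completion rate does not show how many last prescriptions run out inside the month-12 window.

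Most of this stands. It limits the size and shows which reading was meant. It does not remove the contradiction: the sentence and the formula cannot both be followed, and the formula as printed does not do what the missing-data rule suggests.

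Three stronger readings are tempting but not supported.

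- A reader might compare 18.3 with the true 55 in the r = 40 example and infer that every affected constant-dose patient loses at least 18 MED and becomes a false 10-MED responder. That mixes two things. Correcting the denominator alone gives 41.25. The remaining gap arises because supply carried in from before the window is not credited. The denominator effect is under 10 MED on 55% of run-out days with whole prescriptions and on 18% with day-level supply.
- A reader might infer that the treatment comparison is biased. That needs unequal shares between arms, and the documents show none.
- A reader might call crediting by order date an error. It is a definite rule. It does not match the time average in SAP 9.3, but the mismatch adds noise, not bias between arms.

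**Conclusion.** The point holds, and the text should be corrected. The sentence contradicts the formula in the definition of the primary outcome. The printed formula also turns days declared missing into zeros, against the evident intent of the rule beside it.

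The likely consequence is modest: an overstated fall within each arm and a power loss of at most about 2 points at a 10% share. These sizes rest on 55 MED/day, 30-day prescriptions, constant dose, evenly spread run-out days and assumed shares. The true share cannot be obtained from the documents. The reason to act is that two programmers working from the SAP could derive different primary values for the same patient. It remains possible that the specification file resolves this.

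**What to change.** 1. Delete the days-supplied sentence in Protocol 4.1.1 and SAP 9.2, or label that quantity a sensitivity analysis.
2. Change the formula's denominator to the non-missing days in the window. State that G20 no days stay in as zero and that days declared missing are removed.
3. Treat the numerator consistently: say how supply that starts before the window, or runs past the last non-missing day, is counted.
4. Set a minimum number of non-missing days below which the window is missing, for example 30 (one usual prescription). This also defines who counts as missing for the 20% trigger in SAP 9.4, which governs the attrition and tipping-point analyses.
5. If the specification file already fixes these points, copy them into the SAP.

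Day-by-day crediting of supply can be an optional sensitivity analysis, using the prescription dates and supply days already extracted (Protocol 4.1.4). It should not come with a rule that drops baseline days before the first prescription in the window while counting later gaps as zero. In a simulation with assumed mean gaps of 3 to 10 days, that rule created a false decrease of about 1 to 3 MED.

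The cost is wording in two documents and modest reprogramming, with no new data. The drawback is that averages over few days are noisier, which is why a minimum is needed.
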